7.2 Objective Status at Each Disease Evaluation

Objective Status is to be recorded at each evaluation. All measurable lesions up to a maximum of 2 lesions per organ 5 lesions in total, representative of all involved organs, should be identified as *target* lesions at baseline. All other lesions (or sites of disease) including any measurable lesions over and above the 5 target lesions should be identified as *non-target* lesions. Measurements must be provided for target measurable lesions, while presence or absence must be noted for non-target measurable and non-measurable disease.

For studies that use disease progression as an endpoint, whole body scanning at specific intervals is necessary to determine that progression is NOT present outside of the “target” areas. Therefore, in these studies it is not acceptable to image only the “target” areas of the body in follow-up scans. For study-specific imaging requirements, see the Study Calendar in Section 9.0.

- a. **Complete Response (CR):** Complete disappearance of all target and non-target lesions (with the exception of lymph nodes mentioned below). No new lesions. No disease related symptoms. Any lymph nodes (whether target or non-target) must have reduction in short axis to < 1.0 cm. All disease must be assessed using the same technique as baseline.
- b. **Partial Response (PR):** Applies only to patients with at least one measurable lesion. Greater than or equal to 30% decrease under baseline of the sum of appropriate diameters of all target measurable lesions. No unequivocal progression of non-measurable disease. No new lesions. All target measurable lesions must be assessed using the same techniques as baseline.
- c. **Stable:** Does not qualify for CR, PR, Progression or Symptomatic Deterioration. All target measurable lesions must be assessed using the same techniques as baseline.
- d. **Progression:** One or more of the following must occur: 20% increase in the sum of appropriate diameters of target measurable lesions over smallest sum observed (over baseline if no decrease during therapy) using the same techniques as baseline, as well as an absolute increase of at least 0.5 cm. Unequivocal progression of non-measurable disease in the opinion of the treating physician (an

explanation must be provided). Appearance of any new lesion/site. Death due to disease without prior documentation of progression and without symptomatic deterioration (see Section 10.2e).

Notes regarding new lesions: FDG-PET imaging can complement regular scans in identifying new lesions according to the following algorithm.

1. Negative FDG-PET at baseline, with a positive FDG-PET at follow-up is a sign of progression based on a new lesion.
 2. No FDG-PET at baseline and a positive FDG-PET at follow-up corresponding to a potential new site of disease must have a confirmation by anatomical assessment (e.g. CT, MRI, x-ray) as new site of disease to be considered progressive disease. In such a case, the date of progressive disease will be the date of the initial abnormal FDG-PET.
- e. **Symptomatic deterioration**: Global deterioration of health status requiring discontinuation of treatment without objective evidence of progression. Efforts should be made to obtain objective evidence of progression after discontinuation.
- f. **Assessment inadequate, objective status unknown**. Progression or symptomatic deterioration has not been documented, and one or more target measurable lesions have not been assessed or inconsistent assessment methods were used.
- g. Objective status notes:
1. Non-measurable and non-target measurable disease do not affect Objective Status in determination of CR (must be absent--a patient who otherwise has a CR, but who has non-measurable or non-target measurable disease present or not assessed, will be classified as having a PR). However, non-measurable and non-target lesions are included in determination of progression (if new sites of disease develop or if unequivocal progression occurs in the opinion of the treating physician).
 2. An objective status of PR or stable cannot follow one of CR. Stable can follow PR only in the rare case that tumor increases too little to qualify as progression, but enough that a previously documented 30% decrease no longer holds.
 3. In cases for which initial flare reaction is possible (hypercalcemia, increased bone pain, erythema of skin lesions), objective status is not progression unless either symptoms persist beyond 4 weeks or there is additional evidence of progression.
 4. Lesions that appear to increase in size due to presence of necrotic tissue will not be considered to have progressed.
 5. For bone disease documented on bone scan only, increased uptake does not constitute unequivocal progression. However, increase in the soft tissue component of a lesion as measured by CT or MRI would constitute progression.
 6. Appearance of new pleural effusions does not constitute unequivocal progression unless cytologically proven of neoplastic origin, since some effusions are a toxicity related

to therapy or other medical conditions. Increase in the size of an existing effusion does not constitute unequivocal progression, since the fluid status of the patient could alter the size of the effusion.

7. If CR determination depends on a lesion for which the status is unclear by the required tests, it is recommended the residual lesion be investigated with biopsy or fine needle aspirate.

7.3 Best Response

This is calculated from the sequence of objective statuses.

- a. CR: Two or more objective statuses of CR a minimum of four weeks apart documented before progression or symptomatic deterioration.
- b. PR: Two or more objective statuses of PR or better a minimum of four weeks apart documented before progression or symptomatic deterioration, but not qualifying as CR.
- c. Unconfirmed CR: One objective status of CR documented before progression or symptomatic deterioration but not qualifying as CR or PR.
- d. Unconfirmed PR: One objective status of PR documented before progression or symptomatic deterioration but not qualifying as CR, PR or unconfirmed CR.
- e. Stable/no response: At least one objective status of stable/no response documented at least 6 weeks after registration and before progression or symptomatic deterioration, but not qualifying as anything else above.
- f. Increasing disease: Objective status of progression within 12 weeks of registration, not qualifying as anything else above.
- g. Symptomatic deterioration: Objective status of symptomatic deterioration within 12 weeks of registration, not qualifying as anything else above.
- h. Inadequate assessment, response unknown: Progression or symptomatic deterioration greater than 12 weeks after registration and no other response category applies.

8. Statistical methods and determination of sample size

8.1 Sample Size Determination

Overall Survival (OS) at 6 month is the primary endpoint on this study. OS is defined in section 8.2. Dropouts/screen failures defined in section 4.2.2 and those who are lost

follow-up prior to 6 months from starting on trial except death are not evaluable for the primary endpoint, and they will be replaced by new patients. The study will test the null hypothesis of $\leq 30\%$ of OS at 6 month against the alternative of $\geq 50\%$ of OS at 6 month (HR = 0.578 under exponential model). The sample size was determined, based on the Simon's two-stage minimax design. With one-sided 10% of type I error rate and 90% statistical power, a sample of evaluable 39 will be evaluated: 28 in first stage and additional 11 in second stage. If 8 or more out of 28 survive 6 months or more, the study goes on the second stage.. REGORAFENIB will be deemed to have good activity if ≥ 16 out of 39 patients survive 6 months or more from starting on trial. The continuation of accrual may be allowed while the analysis for early stopping being conducted. We expect to accrue 2 or more patients per month among 6-7 participating institutions and will follow up patients 6 months or more.

Dropouts/screen failures defined in section 4.2.2 and those who are lost follow-up prior to 6 months from starting on trial except death, disease and severe toxicity are not evaluable for the primary endpoint, and they will be replaced by new patients

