This is a multi-institutional single arm, *Simon's two-stage* trial using regorafenib as a single agent in patients who have failed at least one prior line of systemic therapy in advanced biliary tumors. 39 patients will be accrued. Patients will receive regorafenib 160 mg QD (21 days on and 7 days off). After 2 cycles (1cycle= 28 days), response and progression will be evaluated using the new international criteria proposed by the revised Response Evaluation Criteria in Solid Tumors (RECIST) guidelines (version 1.1). Primary endpoint is 6 month overall survival.

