4.2.3 Replacement

Dropout patients will need to be replaced.

Patients will be considered inevaluable for the primary endpoint of 6 month of OS if they are not able to complete first cycle. Inevaluable patients will be replaced

5. Treatment[s]

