6.1 Calendar

Required studies must be done within 28 days prior to starting on the treatment.

REQUIRED STUDIES	Pre-Study	Cycle 1 +/- 2 Days				Cycle 2 +/- 2 Days				Cycle 3 ¹ +/- 2 Days				Pre-Progression Follow-Up ¹	Post-Progression Follow-Up ²
		Wk 1	Wk 2	Wk 3	Wk 4	Wk 5	Wk 6	Wk 7	Wk 8	Wk 9	Wk 10	Wk 11	Wk 12		
PHYSICAL ¹															
History and Physical Exam (informed consent)	X	X	X	X	X	X	X			X				X	X
Weight and Performance Status	X	X	X	X	X	X	X			X				X	
Toxicity Notation	X	X	X	X	X	X	X			X				X #	X #
Blood Pressure		X	X	X	X	X	X								
LABORATORY ¹															
CBC, Differential, Platelets	X	X		X		X		X		X					
CA-19-9	X									X					
Serum Chemistry ³	X	X		X		X		X		X					
U/A ⁷	X														
PT/INR	X														
X-RAYS AND SCANS ^{1, 4}															
CT/MRI for Disease Assessment ⁵	X									X				X	
EKG	X														
SPECIMEN SUBMISSION															
Blood sample (for correlatives) ⁶	X									X					
TREATMENT															
Regorafenib		X	X	X		X	X	X		X	X	X			

- 1 Protocol treatment and parameters will continue at these intervals until progression of disease or until patient has met any of the guidelines in Section 4.2.1
- 2 After off treatment following disease progression, physical assessments (with lab tests performed at the discretion of the treating investigator) should take place every 3 months for up to two years or death.
- 3 Sodium, potassium, chloride, CO₂, calcium, magnesium, phosphorus, blood urea nitrogen [BUN], creatinine, glucose, albumin, total protein, alkaline phosphatase, bilirubin [total and direct], AST, ALT

- 4 To be performed every 8 weeks until progression. Must be performed using same method as prestudy.
- 5 Scan must be performed +/- 1 week of each assessment.
- 6 Draw 1 x10mls EDTA tubes at baseline, Cycle 3 Day 1 (+/- 2 days), and at the treatment discontinuation visit if patient continues on after cycle 3 day1. (see section 13.)
7. Spot urine must not show 2+ or more protein in urine or the patient will require a repeat urine analysis. If repeat urinalysis shows 2+ protein or more, a 24- hour urine collection will be required and must show total protein excretion <3500 mg/24 hours

Toxicity should be evaluated until resolution of any adverse events.

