9.6 Further safety

Progressive disease

If progressive disease leads to signs and symptoms that meet the criteria for an SAE (i.e., hospitalization, disability, death, or important medical event), the signs and symptoms should be reported as an SAE and not the underlying progressive disease.

Death

If any subject dies during the trial or within 30 days of the end-of-treatment visit, the investigator will inform Bayer and record the cause of death in detail (using the SAE Form) within 24 hours.

10. Premature termination of the study

- If risk-benefit ratio becomes unacceptable owing to, for example,
 - Safety findings from this study (e.g. SAEs)
 - Results of any interim analysis
 - Results of parallel clinical studies
 - Results of parallel animal studies (on e.g. toxicity, teratogenicity, carcinogenicity or reproduction toxicity).
- If the study conduct (e.g. recruitment rate; drop-out rate; data quality; protocol compliance) does not suggest a proper completion of the trial within a reasonable time frame.

The investigator has the right to close his/her center at any time.

For any of the above closures, the following applies:

- Closures should occur only after consultation between involved parties.
- All affected institutions (e.g. IEC(s)/IRB(s); competent authority (ies); study center; head of study center) must be informed as applicable according to local law.
- In case of a partial study closure, ongoing subjects, including those in post study follow-up, must be taken care of in an ethical manner.

Details for individual subject's withdrawal can be found in Section 4.2.1.

11. Data recording

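### Section 8.1 does not say whether accrual may run through the 6-month wait for the stage-1 result, and Sections 4.2.3 and 8.1 conflict on whether deaths in cycle 1 count

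*Combined protocol and SAP*

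**What the plan says.** Section 8.1 tests 30% against 50% six-month survival with a Simon minimax design of 28 + 11 evaluable patients, one-sided 10% type I error and 90% power. The interim rule is "If 8 or more out of 28 survive 6 months or more, the study goes on the second stage"; activity is declared with at least 16 survivors of 39. On accrual it says "The continuation of accrual may be allowed while the analysis for early stopping being conducted" and "We expect to accrue 2 or more patients per month among 6-7 participating institutions". Section 4 sets the ceiling: "39 patients will be accrued". No sentence covers the interval between the 28th start and that patient's 6-month status. Section 8.2 times only the final analysis.

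Evaluability is stated in three ways:

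- Section 4.2.3: "Patients will be considered inevaluable for the primary endpoint of 6 month of OS if they are not able to complete first cycle". Such patients are replaced, and death is not excepted.
- Section 8.1, first paragraph: dropouts, screen failures and those lost to "follow-up prior to 6 months from starting on trial except death are not evaluable for the primary endpoint". Death is excepted.
- Section 8.1, last paragraph: the same rule, but excepting death, disease and severe toxicity.

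On vital status, note 2 to the Section 6.1 calendar says that physical assessments after progression "should take place every 3 months for up to two years or death". The 24-hour death notice in Section 9.6 applies "If any subject dies during the trial or within 30 days of the end-of-treatment visit".

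**The concern.** Stage 1 exists to limit the number of patients given an inactive drug. With a 6-month endpoint and at least 2 patients per month, about 12 arrivals could compete for the 11 stage-2 places before the 28th patient's status is known. Whether the stop spares anyone therefore depends on an accrual rule that the plan does not state.

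The interim count also needs a settled denominator. If early deaths leave it and are replaced, the observed survival proportion rises with no drug effect. The stage-1 stop then becomes less likely and a false-positive conclusion more likely.

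**Working it through.** **Inputs.** From Section 8.1: p0 = 0.30, p1 = 0.50, n1 = 28, N = 39, continue if at least 8, active if at least 16, exponential survival, accrual of 2 or more per month. Assumed: 3 per month as a second rate, Poisson arrivals, an analysis lasting 1 to 2 months, a reporting delay of 0 to 3 months, and the cycle-1 death rates.

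**The plan's design reproduces.** Exact binomial: P(X ≤ 7 | 28, 0.30) = 0.3648. Type I error is 0.0943 and power 0.9001. Expected N at 30% is 28 + 11 × (1 − 0.3648) = 34.99. Designed saving: 11 × 0.3648 = 4.0 patients.

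**Accrual held during the wait, running only during the analysis.** Saving = 0.3648 × E[max(11 − A, 0)], with A Poisson with mean rate × months.

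- 2 per month: 0.3648 × 9.00 = 3.3 (1 month); 0.3648 × 7.00 = 2.6 (2 months).
- 3 per month: 0.3648 × 8.00 = 2.9 (1 month); 0.3648 × 5.03 = 1.8 (2 months).

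**Accrual running through the wait.**

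- Look at the 28th patient's 6-month date, same formula. At 2 per month the mean of A is 12: 0.3648 × 0.911 = 0.33. At 3 per month it is 18: 0.3648 × 0.057 = 0.02.
- Look as soon as all 28 have died or reached 6 months (simulated): about 0.78 and 0.14.

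**Acting when the result is certain.** Stopping means at most 7 survivors of 28, that is, at least 28 − 7 = 21 deaths before 6 months. Once 21 of the first 28 evaluable patients have died before 6 months, 8 survivors are impossible. Closing accrual then is the existing rule applied earlier, so the error rates do not move. Simulated mean saving at 30%, with accrual running:

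| Deaths known | 2 per month | 3 per month |
|---|---|---|
| at once | 2.4 | 1.3 |
| after a 0 to 3 month delay | 1.5 | 0.5 |

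The delay is uniform and capped at each patient's 6-month date.

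**Why the qualifiers matter.** If deaths at any time among the first 28 were counted, then at 50% survival and 2 per month the 21st death would come before the 39th entry in about 47 to 48% of trials. An active drug would often be closed early.

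**Cycle-1 deaths.** Let d be the share of patients dying in cycle 1. If they are excluded and replaced, true 30% survival becomes 0.30/(1 − d) among those counted. The exponential model gives d = 1 − 0.3^(28/182.6) = 0.169.

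| d | counted survival | P(stop at stage 1) | P(declare activity) |
|---|---|---|---|
| 0 | 0.300 | 0.365 | 0.094 |
| 5% | 0.316 | 0.30 | 0.137 |
| 10% | 0.333 | 0.23 | 0.196 |
| 16.9% | 0.361 | 0.15 | 0.31 |

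This ignores patients who leave cycle 1 alive. Excluding them too would move the figures up or down according to their survival.

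**The case against.** Taken literally, the accrual sentence covers the analysis and not the follow-up before it. On that reading roughly half to four-fifths of the designed saving survives (1.8 to 3.3 of 4.0). The interim rule itself implies that the look comes when 6-month status on 28 evaluable patients is known. Section 9 lets the monitoring committee suspend or close the protocol, and Section 10 lists interim results as a ground for termination. A minimax design minimises the maximum sample size, not the expected one, so the sponsor accepted a modest saving. All of this stands, and it makes the accrual item an optional clarification. It does not supply the missing rule for the wait: neither Section 9 nor Section 10 is tied to the 8-of-28 count.

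A reader might infer more than the documents support:

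- That the stop is nearly worthless. This needs the less literal reading, and 0.3 is not a ceiling even then, because a look once all 28 outcomes are known saves about 0.78 at 2 per month.
- That continued accrual harms the error rates. It does not, provided the 8-of-28 rule is still applied.
- That the true type I error is 0.14 to 0.31. The text does not settle this. Section 4.2.2 does not class a death as a dropout, and Section 8.1 excepts death. The entry criteria (ECOG 0 or 1, life expectancy of at least 12 weeks) may also keep cycle-1 mortality below 16.9%.

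**Conclusion.** The accrual rule for the 6-month wait is missing. Depending on how the gap is filled, the mean saving at 30% survival runs from 0.02 to 3.3 patients against 4.0 by design. Only exposure is at stake here, and by a few patients, so this part is optional. With deaths known at once, the early-closure trigger adds about 1.6 to 2.1 patients at 2 per month (2.4 less 0.78 or 0.33). With a 0 to 3 month delay it adds about 1.2 over a look at the 28th patient's 6-month date (1.5 less 0.33). These figures rest on exponential survival, Poisson entry and the assumed analysis time and delays.

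The evaluability conflict is the more important item because it reaches the primary inference. The stated type I error of at most 10% holds only if deaths in cycle 1 count as events. Replacing them at an assumed 5% cycle-1 mortality already gives 0.137.

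**What to change.** 1. **Evaluability (priority).** Reconcile Section 4.2.3 with both paragraphs of Section 8.1, and state that a death in cycle 1 is an evaluable event, counted at stage 1 and at the final analysis. This is a text change. Fewer patients would be replaced, and the stated error rates would then apply.

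2. **Accrual trigger (optional).** Add to Section 8.1 that accrual closes as soon as 21 of the first 28 evaluable patients, ordered by date of starting on trial, have died before 6 months, and that stage 1 is passed as soon as 8 of those 28 have reached 6 months alive. Keep both qualifiers: before 6 months, and among the first 28 evaluable. Patients counted in either event are already evaluable, so later losses among the others cannot reverse it. N, thresholds, type I error and power do not change. The cost is prompt vital-status reporting on stage-1 patients; monthly checks would be 28 × 6 = 168 without replacements, some falling on scheduled visits.

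3. **The wait (optional).** Say in the same place whether accrual runs or is held after patient 28. A hold is the sponsor's choice. Held until either event in item 2, it restores an expected N of about 35.0 at 30% survival. With immediate knowledge, the mean pause when stage 1 passes at 50% survival is 1.0 month at 2 per month and 2.1 at 3 (2.0 and 3.5 with a 0 to 3 month lag). If a hold to the 28th patient's 6-month date was intended, that pause is already 6 months and the trigger would shorten it.

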8.2 Statistical Analysis

Overall survival (OS) is defined as the time from starting on trial to date of death due to any cause and progression-free survival (PFS) is defined as the duration of time from start of treatment to time of progression or death, whichever comes first. The final analysis will be conducted after the follow-time of the last patient exceeds 6 months. The primary endpoint of the study is OS at 6 month. The experimental treatment will be deemed to have good activity if ≥ 16 out of 39 evaluable patients survive 6 months or more. OS will be estimated using the Kaplan-Meier method and the two-sided 95% confidence interval (CI) for median OS will be computed using log-log transformation.

The secondary endpoints in this study include the disease control response (DCR) defined as (CR + PR+ SD), toxicity, and PFS. DCR rate will be reported with 95% CI computed by the Clopper-Pearson method. The frequency and severity of adverse events and tolerability of the regimen will be summarized using descriptive statistics. PFS with 95% CI will be estimated. As exploratory objective, the association between biomarkers and clinical outcomes (DCR rate, OS and PFS) will be examined using multiple logistic regression and the multivariable Cox regression model. A p-value of < 0.05 will be considered statistically significant. Frequency and severity of adverse events will be summarized using descriptive statistics.

9. Safety Monitoring

Safety assessments will consist of monitoring and recording all adverse events and serious adverse events, the regular monitoring of hematology and blood chemistry parameters and regular physical examinations. Adverse events will be evaluated continuously throughout the study. Safety and tolerability will be assessed according to the NIH/NCI Common Terminology Criteria for Adverse Events version 4.0 (CTCAE v4.0) that is available at:

<http://evs.nci.nih.gov/ftp1/CTCAE/About.html>

The PMC monitors its assigned ongoing research protocols for: adverse event reporting, data and safety monitoring, and internal audit findings. The PMC, upon review of any

agenda item, may approve the study for continuation, require revisions, suspend or close a protocol.

Investigators of studies, which are designated to be reviewed by the PMC for data and safety monitoring, shall provide a statistical report of the study's progress and summary of adverse events and deviations based on the phase of the study and the associated risk of the study or

more often if applicable. The external DSMB (if applicable) shall forward its report for high-risk studies designated for external review at least annually or more often if applicable.

Internal Monitoring Plan

Data will be captured in Oncore, Moffitt's Clinical Trials Database. Regulatory documents and case report forms will be reviewed routinely according to Moffitt's Monitoring Policies.

